4.4. Image Analysis of *anti-[¹⁸F]FACBC* PET-CT

The methods of image analysis to be used for the *anti-[¹⁸F]FACBC* PET-CT are as follows:

- 1) Images will be reconstructed with iterative technique and hardware fused (PET to CT) on a MimVista or similar workstation which enables SUV (mean, maximum, total lesion activity) as well as standard size measurements of lesions. An edge seeking conformational volume of interest tool as appropriate (PET Edge, MIMvista, Cleveland, OH) will typically utilized. If this is not possible due to anatomy an appropriate 2D or 3D ROI will be utilized.
- 2) Visual inspection of the PET-CT images by a board certified nuclear medicine imager who will be blinded to all history and other imaging.
- 3) For *anti-3-[¹⁸F]FACBC*, uptake will be defined according to the following criteria in relation to background structures: mild (above blood pool but less than marrow), moderate (above or equal to marrow but less than liver), and intense (equal to or above liver). Visual analysis will be aided by quantitative criteria of SUV_{max} lesion/ SUV_{mean} background. Maximum and mean SUV of each focus of abnormal uptake as well as background structures including liver, marrow at L3, aorta, and bladder will be recorded. For prostate beds as well as extra-prostatic sites such as lymph nodes and bone, abnormal moderate or intense focal uptake over background marrow which persist from early to delayed images will be considered prospectively positive. These criteria were used to analyze data in our study of *anti-[¹⁸F]FACBC* in recurrent disease.
- 4) Confidence in interpretation for disease within the prostate bed and outside the bed will be recorded with the following scale on a per patient basis and any all recordable lymph nodes: 1 - definitely negative; 2 - probably negative; 3 - indeterminate; 4 - probably positive; 5 - definitely positive.
- 5) In summary, we will record both visual and semi-quantitative analysis of the prostate bed, positive lymph nodes (greater than blood pool), and other structures such as skeletal foci on early and delayed time frames. We will use maximum and mean SUV as well as standard bidimensional size measurements. We will also record similar measurements on background structures such that we may derive uptake ratios.

4.5. Clinical and Histological Assessment.

After the *anti-[¹⁸F]FACBC* scan has been obtained and interpreted, the following will occur:

- 1) All patients with identifiable sites of disease on FACBC PET will, if clinically feasible, undergo targeted fusion biopsy followed by the standard TRUS-guided biopsy. The targeted biopsy will be performed before the standard TRUS-guided biopsy because patient motion and movement may affect the accuracy of the targeted biopsy and because the standard TRUS-guided biopsy is a random biopsy and does not have a high requirement on patient motion. If this is not deemed appropriate by the clinical team and referring Urologist or Radiation Oncologist, patients will undergo standard TRUS 12-core biopsy as clinically appropriate.

- 2) All pathologic samples will undergo standard analysis to determine if prostate carcinoma cells are present as well as (if there is sufficient tissue) provide tissue for Aim 1. Specimens will be fixed in neutral-buffered formalin, embedded in formalin, sectioned at 5-micron thickness and stained with hematoxylin & eosin (H&E) using standard pathology procedures. Board-certified anatomic pathologists from Emory University will perform all diagnosis of prostate carcinoma (and when applicable Gleason grading and staging) using standard criteria.
- 3) As a secondary endpoint, patients with abnormal extraprostatic suspicious findings on *anti-[¹⁸F]FACBC* PET-CT may have those suspicious lymph nodes or other extraprostatic sites sampled as clinically appropriate through a combination of percutaneous image guided needle biopsy, laparoscopic techniques, as well as open lymph node dissection when appropriate. With both laparoscopic and open nodal dissections, it is standard practice to also sample adjacent imaging negative nodes. Rare sites of suspect metastases such as the inguinal nodal regions will be evaluated via a combination of physical exam and percutaneous biopsy as appropriate. Due to the high PPV of FACBC for extraprostatic disease, at the least, the referring clinician will discuss the findings with the patient and offer biopsy or other diagnostic investigations (such as advanced bone imaging for suspected skeletal lesions) as deemed clinically appropriate. In the event that the PET/CT demonstrates that the prostate cancer may have spread to areas outside of the prostate, the referring urologist or primary care physician will be notified and the findings will be discussed with the patient.

4.6. Statistical Analysis

The PI consulted with [name] at the Winship Statistical ^{Co}re. The following description was provided by [name] for the analysis plan and sample size.

Analysis Plan: After we obtain the pathological results for each core from the standard TRUS-guided biopsy and the PET/TRUS fusion targeted biopsy, we will calculate the cancer detection rate per core. For example, we will calculate how many cores are able to detect prostate cancer in the standard TRUS-guided biopsy and how cores will detect cancers in the PET/TRUS-guided biopsy. Based on the total numbers of cores for each biopsy approach, we can calculate the cancer detection rate per core for each biopsy approach. In order to compare the detection rates between the PET positive and negative groups, Chi-square test will be used to compare the detection rates with standard biopsy between the two arms with FACBC scan positive and negative, respectively. Logistics will be further employed to test their adjusted effect after adjusting for other factors in the multivariate analysis. In the first specific aim, the goal is to determine if the PET/TRUS fusion targeted biopsy can detect more prostate cancer than the standard TRUS-guided biopsy. Therefore, among the FACBC positive arm, Kappa coefficient will be calculated to measure the correlation of the paired diagnostic results between the standard biopsy and the fusion targeted biopsy. McNemar's test will be further used to test on its significance.

Sample Size: We will recruit a total of 36 patients for this study. According to the inclusion criteria, approximately half of patients will have positive imaging scans and the other half negative. We determine the sample size in order to compare the performance of standard biopsy with the fusion targeted biopsy. We will expect to have 18 patients with FACBC positive, therefore, with McNemar's test, the sample size of 18 paired samples will achieve a power of at least 80% to detect a Kappa coefficient of 0.62 or higher between the two methods at the significant level of 0.05, assuming equal probability of positive or negative diagnosis outcome. We also like to determine the power to compare the detection rates of standard TRUS-guided biopsy between the PET positive and negative groups. With 18 FACBC positive patients and 18 FACBC negative patients, this study will have a power of at

least 80% to detect a difference in detection rates of 41% or higher between the two groups at the significant level of 0.05.

5. Registration/Randomization

Patients will be registered and consented into the study by one of the research nurses on staff working in the clinical Urology or Radiology setting. There will be no randomization. Patients are referred to the study by an Emory physician and or Co-I via email or telephone. Patient is seen at next appointment or at FACBC PET scan visit. Patient is then consented, registered into ERMS and eligibility criteria completed.

6. Intervention

This is not a therapeutic study. Diagnosis only.

Standard transrectal ultrasound (TRUS) guided biopsy: An ultrasound probe about 2.5 cm in diameter is gently inserted into the rectum. This ultrasound probe allows visualization of the prostate on two-dimensional (2D) images and allows for the placement of a biopsy needle that collects samples of the prostate. Usually, a total of 12 biopsy specimens are usually collected. The procedure takes about 20 minutes. This TRUS-guided biopsy is considered as the standard method for prostate cancer diagnosis. However, this biopsy procedure randomly takes tissue specimens from the prostate. Because of sampling errors, this standard TRUS-guided biopsy may miss the tumor in the prostate. In this proposed study, we will use three-dimensional (3D) ultrasound imaging to guide the biopsy in order to improve the location of the biopsy needle and will also use PET imaging to direct the biopsy to a suspicious target. The 3D ultrasound guided biopsy procedure is outlined in the next paragraph.

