The hypothesis of the study is that FACBC PET/ultrasound fusion targeted biopsy can detect more cancer per core than the standard 12-core TRUS guided biopsy. The specific aims include: 1) To perform FACBC PET/CT directed, 3D ultrasound-guided biopsy and determine if fusion targeted biopsy can detect more cancers than 2D TRUS-guided biopsy; and 2) To develop the workflow for performing deformable registration and fusion of FACBC PET/CT and 3D ultrasound images of human patients. Thirty six patients, who have suspicion of recurrent prostate cancer after definitive therapy such as radiotherapy, will be recruited into this study. At least half of the patients will have positive imaging findings and will undergo 2D TRUS-guided biopsy as well as PET/ultrasound fusion biopsy. The proposed study will be the first-in-human trial that uses PET/CT imaging to direct 3D ultrasound-guided biopsy of the prostate. The multimodality imaging approach will combine the high sensitivity from PET and real-time information from ultrasound for improved cancer detection.

This early-phase clinical trial will help transform the field from the current “blind” biopsy to future “targeted” biopsy and result in the change of prostate cancer management. The new biopsy technology can have an immediate impact on patient care by improving the detection and diagnosis of prostate cancer.

1. Background and Significance

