Central Hypothesis: FACBC PET/ultrasound fusion guided biopsy can detect more cancer per core than the standard 12-core TRUS-guided biopsy. The specific aims include:

Aim 1: To perform FACBC PET/CT directed, 3D ultrasound-guided biopsy and to determine if fusion targeted biopsy can detect more cancer per core than standard TRUS-guided biopsy.

We will recruit 36 patients who have suspicion of recurrent prostate cancer after definitive therapy such as radiotherapy or other non-prostatectomy focal therapy such as cryotherapy. Based on our clinical experience, at least half of the patients (N≈18) will have positive imaging findings in the prostate bed. These patients will undergo a standard 12-core systematic biopsy followed by PET/ultrasound fusion targeted biopsy at the same setting. Patients with negative scan will undergo the standard biopsy. We will determine (i) whether fusion targeted biopsy can detect more cancer per core than the standard biopsy; (ii) whether the addition of targeted biopsy to systematic biopsy increases the rate of diagnosis of Gleason 7 or greater cancer.

The patient will be in the same setting for the standard TRUS-guided biopsy and the PET/TRUS fusion targeted biopsy. The same setting allows us to directly compare the accuracy of the two biopsy approaches for the same patients. This sequential study is supported by the literatures. For example, the NIH team led by [name] is one of the pioneer groups in the field of MRI/TRUS fusion

targeted biopsy. In their study, "*Patients in the trial underwent a standard of care 12-core TRUS biopsy and MRI/US fusion guided biopsy in the same setting.*" (P.A. Pinto, P.H. Chung, A.R. Rastinehad, A.A. Baccala, Jr., J. Kruecker, C.J. Benjamin, S. Xu, P. Yan, S. Kadoury, C. Chua, J.K. Locklin, B. Turkbey, J.H. Shih, S.P. Gates, C. Buckner, G. Bratslavsky, W.M. Linehan, N.D. Glossop, P.L. Choyke, B.J. Wood, "Magnetic resonance imaging/ultrasound fusion guided prostate biopsy improves cancer detection following transrectal ultrasound biopsy and correlates with multiparametric magnetic resonance imaging," *The Journal of urology* 186, 1281-1285, 2011).

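### The central hypothesis is per core, but section 4.6 gives it no test or interval; the only targeted-versus-standard test is a patient-level McNemar

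*Combined protocol and SAP*

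**What the plan says.** The Precis/Abstract states the hypothesis as "FACBC PET/ultrasound fusion targeted biopsy can detect more cancer per core than the standard 12-core TRUS guided biopsy". Section 3 (Specific Aims) repeats it as the central hypothesis, words Aim 1 per core, and lists as question (i) "whether fusion targeted biopsy can detect more cancer per core than the standard biopsy".

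Section 4.6 plans pathology for each core, then says: "Based on the total numbers of cores for each biopsy approach, we can calculate the cancer detection rate per core for each biopsy approach". Nothing more is said about comparing the two rates. The section then restates the first aim with no mention of cores: "the goal is to determine if the PET/TRUS fusion targeted biopsy can detect more prostate cancer than the standard TRUS-guided biopsy". For that aim the plan says "among the FACBC positive arm, Kappa coefficient will be calculated to measure the correlation of the paired diagnostic results between the standard biopsy" (set against each man's targeted result), with McNemar's test to follow. The sample-size paragraph fixes the unit: 18 FACBC-positive patients give 18 paired samples.

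The chi-square test and the logistic model in section 4.6 concern standard-biopsy detection in PET-positive against PET-negative men. They do not compare targeted with standard biopsy.

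Section 6 gives 12 as the usual number of standard specimens. No section gives a number of targeted cores.

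**The concern.** The hypothesis and its test use different units. McNemar compares whether any of about 12 standard cores was positive with whether any of an unstated number of targeted cores was positive. With unequal numbers of cores, that patient-level comparison and the per-core comparison can point in different directions.

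Two things are at stake. First, the central hypothesis has no pre-specified inference, so any per-core test or interval would be chosen after the data are seen. Second, a reader could take the McNemar result as the answer to the per-core question. It could be null when targeted cores are much richer in cancer, or favour standard biopsy when the per-core rates are equal.

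The per-core sentence is also loose about whose cores count. Section 3 says "Patients with negative scan will undergo the standard biopsy", and section 4.5 allows some PET-positive men to have only the standard biopsy.

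**Working it through.** **The plan's own power figure.** The stated figure is at least 80% power with 18 pairs, kappa 0.62 and alpha 0.05, "assuming equal probability of positive or negative diagnosis outcome". It reproduces as a two-sided test of kappa = 0 with both marginals 0.5:

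power = Φ[(0.62 − 1.96·√(1/18)) / √((1 − 0.62²)/18)] = Φ[(0.620 − 0.462)/0.185] = Φ(0.855) = 80.4%.

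This is a patient-level statement about agreement. It contains no per-core rate, core count or within-man correlation, so it says nothing about the per-core contrast.

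**Inputs for the illustration.** From the documents: 18 men with both biopsies, 12 standard cores each, alpha 0.05 (two-sided assumed). Not in the documents, and assumed: m = 2, 3 or 4 targeted cores, the per-core rates, and an intra-man correlation (ICC) of 0 or 0.3 under a beta-binomial model with α = p(1−ICC)/ICC and β = (1−p)(1−ICC)/ICC. The two methods are taken either as independent within a man or as sharing the patient effect (the same quantile for both). McNemar is exact, by enumeration.

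**Case A: each method positive in 50% of men.** This applies the plan's 50% assumption to both methods, so McNemar's null is true by construction. With independent cores, 1 − (1−p)^m = 0.5 gives p = 1 − 0.5^(1/m):
- standard, m = 12: 5.6%
- targeted, m = 2, 3, 4: 29%, 21%, 16%

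At ICC 0.3 the rates are 14% standard against 34%, 27%, 24% targeted. The per-core hypothesis is true throughout. If the methods are independent within a man, each discordant cell is 0.5 × 0.5 = 0.25, and McNemar is significant in favour of targeted in 1.1% of trials. With the shared patient effect at ICC 0.3, the figure is 0.25% to 0.37%.

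**Case B: equal per-core rates, ICC 0.3.** The hypothesis is false, but 12 cores have more chances to hit than 2 to 4. The last two columns give the share of trials in which McNemar is significant in favour of standard.

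| Per-core rate, both methods | Men positive: standard vs targeted (m = 2, 3, 4) | Methods independent | Shared effect |
|---|---|---|---|
| 5.6% | 23% vs 9%, 12%, 14% | 3–7% | 1–4% |
| 14% | 50% vs 23%, 29%, 33% | 9–25% | 9–34% |
| 30% | 79% vs 45%, 54%, 60% | 12–40% | 13–55% |

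The men-positive column is 1 − ∏(β+j)/(α+β+j) over j = 0 to m−1.

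**What 18 men could say per core.** With methods independent within a man, the approximate 95% half-width for the difference is

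2.11 · √[p_T(1−p_T)(1+(m−1)ICC)/(18m) + p_S(1−p_S)(1+11·ICC)/216].

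For m = 2 and ICC 0.3: 2.11·√[0.342·0.658·1.3/36 + 0.142·0.858·4.3/216] = 2.11·√(0.00813 + 0.00243) = 0.217. Over the Case A settings:
- ICC 0: 16, 12, 10 points, against true differences of 24, 15, 10
- ICC 0.3: 22, 19, 18 points, against true differences of 20, 13, 9

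A fully shared patient effect narrows the ICC 0.3 half-widths to about 15, 12 and 10 points (by simulation).

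**The case against.** Four points can fairly be made for the plan.

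- **McNemar does match one version of the aim.** The Abstract's Aim 1 asks whether fusion biopsy finds more cancers, without reference to cores, and section 4.6 restates it in the same sense. A reader might infer that Aim 1 has no valid test at all. The documents do not support that: the patient-level goal has a suitable test, and the gap is in per-core inference.
- **Pooling over all men is not proposed.** A reader might infer that PET-negative men's standard cores will enter the standard rate. Taken literally, the sentence about total cores permits it, and it would bias towards targeted biopsy if standard cores yield less in PET-negative men. But section 3 stresses direct comparison in the same patients, and section 4.6 places the paired comparison in the FACBC-positive arm. The wording needs tightening; a planned bias is not shown.
- **No unclustered core-level test is proposed either.** The chi-square in section 4.6 is for standard biopsy between PET groups, so the plan cannot be charged with running a naive chi-square over cores.
- **The study is early-phase and first-in-human, and the illustration rests on assumed inputs.** Both are true. With independent cores, the Case B percentages would run as high as 91%, but independence within one prostate is hard to defend and the point does not rest on it.

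None of this supplies the missing inference. Aim 1 is to determine whether one per-core rate exceeds the other, and two point estimates cannot do that. McNemar cannot be read as the per-core test, since targeted and systematic cores have no one-to-one pairing.

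**Conclusion.** The concern holds, and from the text alone: the central hypothesis, Aim 1 and Aim 1(i) are per core; section 4.6 only calculates pooled per-core rates; and its sole targeted-versus-standard test is at patient level. The simulations are not needed to establish the mismatch.

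Its size depends on inputs the documents do not give. Under the assumptions above, McNemar favours targeted in about 0.3% to 1.1% of trials in settings where the per-core advantage is 9 to 24 points. It favours standard in 1% to 55% of trials when per-core rates are equal and ICC is 0.3. These figures show that the two questions can have different answers. They do not predict this trial's result, and they do not show that a per-core test would be well powered: the expected intervals are about as wide as the differences assumed.

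**What to change.** In section 4.6:

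1. Make the Aim 1(i) analysis the difference in per-core detection rate, targeted minus standard, among PET-positive men who have both biopsies, using only those men's cores.
2. Give a 95% CI and a test that treat the man as the unit. Paired per-man positive-core fractions, a patient-level bootstrap or sign-flip, or a clustered model with a small-sample correction would each serve. Do not use an unclustered core-level test. Check the chosen method at 18 men: in simulation the percentile bootstrap covered 86–94%, and a sign-flip of each man's contribution to the pooled difference reached 12% error towards standard in one sparse setting.
3. Report the numbers of targeted and standard cores for each man.
4. Keep McNemar for the patient-level goal, and align the aim wording in the Abstract, section 3 and section 4.6 so that each goal has its own analysis.
5. State that the existing power figures do not apply to the per-core contrast, and give its expected CI width over a stated range of core counts and ICC.

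Alternatively, restate the central hypothesis and Aim 1(i) per patient to match McNemar, and report per-core rates as descriptive.

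The cost is wording, slightly more analysis work and a less favourable statement of what 18 pairs support. Section 4.6 already plans pathology for each core, so no new patients or data are needed.

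### Section 4.6 does not settle whether the PET-positive versus PET-negative comparison is per core or per man, and makes no allowance for clustering if it is per core

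*Combined protocol and SAP*

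**What the plan says.** All the relevant text is in section 4.6 of the combined protocol and SAP.

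- **Definition of the rate.** The analysis plan counts cancer-bearing cores under each technique and divides: "Based on the total numbers of cores for each biopsy approach, we can calculate the cancer detection rate per core for each biopsy approach". No other detection rate is defined, and nothing says when a man counts as positive on standard biopsy.
- **Test.** For the scan-positive and scan-negative groups, "Chi-square test will be used to compare the detection rates with standard biopsy between the two arms". The sentence does not say whether the rate is per core or per man.
- **Adjusted analysis.** A logistic model is to follow. Its unit is not named, and it has no random effect, GEE structure or robust variance.
- **Power.** The sample-size paragraph turns to the same comparison and counts patients: "With 18 FACBC positive patients and 18 FACBC negative patients". For those numbers it claims 80% power or more, with alpha 0.05, for "a difference in detection rates of 41% or higher between the two groups". It gives neither a baseline rate nor sidedness.

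Section 6 says that a standard biopsy usually yields 12 specimens.

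**The concern.** An analyst looking for the rate that goes into the chi-square test finds only one definition, and it is per core. The central hypothesis is also worded per core. Applying that definition to the group comparison would set about 18 × 12 = 216 cores against 216, as if they were independent. Cores from one prostate share the same disease, so they are correlated. The p-value would be too small, and the study could declare that FACBC status predicts standard-biopsy yield when it does not.

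That would also not be the test whose power is stated. And with the unit left open, it could be chosen after the results are known, when the two choices may lead to opposite conclusions.

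**Working it through.** **Inputs.** From the documents: 18 versus 18 patients, a 41-point difference, at least 80% power, alpha 0.05 (section 4.6), and about 12 standard cores per man (section 6). Assumed: a two-sided test, except where one-sided is stated, and the within-man ICC of core results, which the documents do not give. I show 0.05 to 0.4.

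**Step 1. Which unit does the stated power fit?** With n per group, rates p1 and p2, difference d and mean rate p̄:

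power = Φ{ [d√n − 1.96√(2p̄(1−p̄))] / √(p1(1−p1) + p2(1−p2)) }

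For 18 men per group, 10% versus 51%: d√n = 0.41 × 4.243 = 1.739; 1.96 × √(2 × 0.305 × 0.695) = 1.276; the denominator is √(0.0900 + 0.2499) = 0.583. The power is Φ(0.795) = 78.7%.

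| Rates | Two-sided power, 18 v 18 men | Exact power, uncorrected chi-square |
|---|---|---|
| 5% v 46% | 83.6% | 86.7% |
| 10% v 51% | 78.7% | 80.3% |
| 29.5% v 70.5% | 70.8% | 75.8% |
| 50% v 91% | 79.5% | 81.2% |

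One-sided power is 81.4% or more at every baseline tried. The plan's figure therefore reproduces per man at some baselines two-sided, and at all of those tried one-sided. (The shortfall at mid-range baselines is a separate matter.)

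With 216 versus 216 independent cores, the same formula gives power of essentially 100% for 41 points. The difference detectable with 80% power would be about 13 points for rates centred on 50%. So the 41-point figure was computed on men.

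**Step 2. What happens if cores are pooled?** With m = 12 cores per man:

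- design effect DE = 1 + (12 − 1) × ICC
- actual type I error = 2 × [1 − Φ(1.96/√DE)]

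For ICC 0.1: DE = 1 + 1.1 = 2.1; 1.96/√2.1 = 1.353; type I error = 17.6%. The 18 × 2 × 12 = 432 cores then carry the information of 432/2.1 ≈ 206. At ICC 0.4 the figure is 432/5.4 = 80.

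| Assumed ICC | DE | Type I error, formula | Type I error, simulated |
|---|---|---|---|
| 0.05 | 1.55 | 11.5% | 11.3-11.7% |
| 0.1 | 2.1 | 17.6% | 17.4-18.0% |
| 0.2 | 3.2 | 27.3% | 27.2-27.8% |
| 0.3 | 4.3 | 34.5% | 33.9-35.1% |
| 0.4 | 5.4 | 39.9% | 39.7-40.8% |

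The simulation is beta-binomial, with 18 versus 18 men, 12 cores each, equal true per-core rates of 10-50%, 40,000 runs per setting and an uncorrected chi-square. With a continuity correction it still gives 14.0-15.4% at ICC 0.1 and 36.9-38.1% at 0.4.

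**Step 3. What happens if the test is per man?** By exact enumeration at 18 versus 18 with equal true rates of 20-70%, the uncorrected chi-square has a size of about 4.8-6.5%. Fisher's exact test has about 2-3%.

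**Step 4. Are these ICC values extreme?** Sections 1.2 and 2 say that 70-80% of prostate biopsies are negative. With 12 independent cores that needs a per-core rate of only 1 − 0.8^(1/12) = 1.8% to 1 − 0.7^(1/12) = 2.9%. At an assumed per-core rate of 5%, a beta-binomial model needs an ICC of about 0.14-0.33 to give 70-80% negative biopsies. Those biopsies come from a general population, not from men with suspected recurrence. This shows only that the range is not far-fetched; it does not estimate the ICC here.

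**The case against.** The best defence is that the plan means a per-man test and merely fails to say so. The per-core rate is introduced for standard against fusion biopsy, the chi-square sentence opens a different comparison, and it does not contain the words per core. Both power statements in section 4.6 count patients, and Step 1 shows that the 41-point figure makes sense only for men. On that reading the error rate is near nominal.

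Much of this stands. A reader might infer that the plan prescribes a pooled-core chi-square and so carries a false-positive rate of 18-41%. The documents do not support that: the test's unit is unstated, the power paragraph points to patients, and the ICC is an outside assumption. The figures also assume exactly 12 cores per man and an even split, whereas 12 is only the usual number and 18 per group is an expectation.

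A reader might also infer that the central hypothesis is at risk. It is not, by this route. Aim 1 asks whether fusion biopsy finds more cancer per core than standard biopsy, and whether adding it raises diagnosis of Gleason 7 or greater cancer. Standard-biopsy yield by scan result is neither question.

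What the defence does not supply is a per-man definition of detection. The only rate that section 4.6 defines is per core, and no clustering method guards against its use. That is more than a missing detail.

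**Conclusion.** The concern holds as an inconsistency about the unit of analysis, not as a prescribed error. The rate is defined per core, the test and logistic model have no stated unit, and the power is per man.

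The size is conditional. If cores were pooled as independent at about 12 per man, type I error would be about 12% at an assumed ICC of 0.05 and about 18-41% at an assumed ICC of 0.1-0.4, against a nominal 5%. On a per-man test it stays near 5%, at most about 6.5% at the rates tried. Because the comparison is secondary and the power paragraph already indicates the likely intention, the severity is modest. The plan should still be clarified before the data are analysed.

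**What to change.** Add two sentences to section 4.6:

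1. The chi-square test and the logistic model comparing scan-positive with scan-negative patients take the man as the unit. Standard biopsy is positive if at least one standard core contains cancer. This matches the 18 versus 18 power statement.
2. Any between-group comparison of per-core rates treats the man as the cluster, for example by a beta-binomial model, GEE with a small-sample correction, or permutation of PET status across men.

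The cost is wording only; no new data are needed, because the per-core pathology already yields the per-man result. The downside is that an honest per-core comparison will have wider intervals than pooled cores would suggest, and that a per-man logistic model on 36 men can carry few covariates.

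### With 36 men and no limit on covariates, the adjusted logistic model in 4.6 tends to overstate the PET odds ratio, and has no rule for an empty cell

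*Combined protocol and SAP*

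**What the plan says.** Section 4.6, Analysis Plan, states that a "Chi-square test will be used to compare the detection rates with standard biopsy between the two arms", meaning the men with positive and negative FACBC scans. The next sentence adds the adjusted analysis: "Logistics will be further employed to test their adjusted effect after adjusting for other factors in the multivariate analysis". Section 4.6 does not list the other factors, cap their number, say how the model is fitted, or say what happens if one group has no positive (or no negative) man.

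The Sample Size paragraph sizes this comparison in men, 18 per scan group, and puts its power at "least 80% to detect a difference in detection rates of 41% or higher between the two groups", with alpha set to 0.05. It gives no base detection rate and does not say whether the test is one- or two-sided. The only rate assumption in the section, "assuming equal probability of positive or negative diagnosis outcome", belongs to the kappa and McNemar calculation. The even split rests on the expectation that "approximately half of patients will have positive imaging scans and the other half negative". Section 5 confirms that there is no randomisation.

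**The concern.** The two scan groups are not randomised, and this model is the only adjusted comparison of them in the plan. A reader will take the adjusted odds ratio as the association of scan result with biopsy detection after allowing for other differences between the men.

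Maximum-likelihood logistic regression is biased away from no effect when the rarer outcome is scarce relative to the number of coefficients. The bias grows with each covariate, even one unrelated to outcome. If one group has an empty outcome cell, no finite estimate exists; software may then print a very large odds ratio with a meaningless Wald test, and the analyst has to choose a remedy after seeing the data. Because the plan speaks of factors in the plural and sets no ceiling, two or more covariates is the natural reading. Naming them in advance would not by itself remove the bias.

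**Working it through.** **Inputs from section 4.6.** 36 men, 18 v 18; difference 41 points; alpha 0.05; power at least 80%. Base rates, sidedness and number of covariates are not given, so ranges are shown.

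**The plan's power figure.** For the pooled two-proportion test with n = 18 per group, power = Φ{[0.41 − z·√(2p̄(1−p̄)/n)] / √[(p₀(1−p₀)+p₁(1−p₁))/n]}.

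- 9% v 50%, two-sided: p̄ = 0.295; [0.41 − 1.96 × 0.152] / 0.136 = 0.825; power 0.795. The mirror image, 50% v 91%, gives the same.
- 29.5% v 70.5%, two-sided: p̄ = 0.5; [0.41 − 1.96 × 0.167] / 0.152 = 0.548; power 0.708.
- One-sided power: 0.909 at 5% v 46%, 0.881 at 9% v 50%, 0.814 at 29.5% v 70.5%.

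So the 41-point figure reproduces two-sided near 9% v 50% (or its mirror image), where the difference detectable with 80% power is 41.3 points. If the test is one-sided, at least 80% power holds at every rate tried and the figure says nothing about the base rate.

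**Empty cell.** P(no positive among 18 PET-negative men) = (1 − p₀)^18:

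- 5%: 0.95^18 = 40%
- 9%: 0.91^18 = 18%
- 15%: 0.85^18 = 5%
- 29.5%: 0.705^18 = 0.2% (doubling this to allow for an all-positive PET-positive group still gives 0.4%)

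At 9% v 50% the expected number of positive men is 18 × 0.09 + 18 × 0.50 = 1.6 + 9 = 10.6.

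**True odds ratios with no covariate effect.** 9% v 50%: (0.50/0.50)/(0.09/0.91) = 10.1. 29.5% v 70.5%: (0.705/0.295)² = 5.7.

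**Simulation.** 1,500 data sets per setting, one record per man. Covariates were a mix of standard normal and 30%-prevalence binary, independent of PET, each with log odds ratio 0 (null) or 0.5. The true value rises when covariates carry an effect because the odds ratio is then conditional on them. ML = maximum likelihood.

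| Rates | Covariates | True OR | ML: PET OR infinite | ML: median of finite ORs | ML: infinite or >2× true | Firth median | Firth >2× true |
|---|---|---|---|---|---|---|---|
| 9% v 50% | 0 | 10.1 | 19% | 10.0 | 33% | 9.4 | 20% |
| | 1 (0.5) | 11.2 | 18% | 11.1 | 36% | 10.0 | 22% |
| | 2 (null) | 10.1 | 20% | 11.2 | 39% | 9.0 | 22% |
| | 3 (0.5) | 12.6 | 20% | 15.6 | 47% | 10.7 | 24% |
| | 4 (null) | 10.1 | 21% | 13.4 | 46% | 9.1 | 24% |
| | 5 (0.5) | 14.1 | 21% | 24.1 | 55% | 11.4 | 22% |
| 29.5% v 70.5% | 0 | 5.7 | 0.5% | 6.2 | 23% | 5.5 | 14% |
| | 1 (0.5) | 6.3 | 0.3% | 7.2 | 27% | 5.9 | 17% |
| | 2 (null) | 5.7 | 1.1% | 6.8 | 30% | 5.4 | 19% |
| | 3 (0.5) | 7.0 | 1.3% | 10.2 | 39% | 6.9 | 21% |
| | 4 (null) | 5.7 | 1.1% | 8.0 | 36% | 5.4 | 18% |
| | 5 (0.5) | 7.8 | 2.8% | 13.0 | 46% | 7.1 | 22% |

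A separate run with null covariates only gave finite medians of 10.4 with one covariate and about 11.4 to 14.4 with two to five at 9% v 50%, and about 6.5 to 8.3 with two to five at 29.5% v 70.5%. Further null-covariate runs put the five-covariate value somewhat higher: 15.0 to 17.0 at 9% v 50%, and 9.0 at 29.5% v 70.5%. Firth estimates were finite throughout.

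**The case against.** A reader might infer that, under the plan's own assumptions, the adjusted odds ratio would often be infinite. The documents do not support that. They give neither base rate nor sidedness for the 41-point comparison, and carrying the 50% from the McNemar sizing across is a choice of the reader. With a one-sided test the stated power holds at mid-range rates, where infinite estimates almost vanish. Even at 9%, about four trials in five give a finite estimate.

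A reader might also infer that the method breaks down at this sample size whatever is adjusted for. With one covariate it does not: the finite median is 11.1 against 11.2 at 9% v 50%, and 7.2 against 6.3 at 29.5% v 70.5%. The harm there is mainly the empty cell. Nor is the test necessarily lost, since 4.6 asks for a test of the adjusted effect and specifies no Wald statistic. In 2,000 simulated trials per setting with one null covariate, the likelihood-ratio test had 83% power against 61% for Wald at 9% v 50%. Its type I error was about 7% with both groups at 29.5%, rising to about 9% with five covariates. That is imperfect but usable.

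The per-man unit is also an inference. The Analysis Plan opens with detection per core, and with usually 12 cores per man (section 6) a core-level model would have about 36 × 12 = 432 records. Sparse cells would matter less there, but clustering within men would then need handling, and 4.6 does not mention it.

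Finally, part of the exceedance in the table is plain imprecision: with PET status alone, 23% to 33% of estimates are already infinite or more than twice the truth.

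These points limit the concern. What remains is the inflation with two or more covariates, which appears at mid-range rates too and so does not depend on the 9% assumption.

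**Conclusion.** The point holds in a limited form. On the per-man reading, ordinary maximum likelihood with two or more covariates tends to overstate the adjusted PET odds ratio at both pairs of rates in the table. The median finite estimate exceeds the truth by roughly 15% to 45% with two to five null covariates at 29.5% v 70.5% (6.5/5.7 = 1.14; 8.3/5.7 = 1.46), and by a similar proportion at 9% v 50% (11.4/10.1 = 1.13; 14.4/10.1 = 1.43). It exceeds the truth by more when several covariates carry real effects.

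The non-finite estimate, at about 18% of trials, is conditional on a PET-negative detection rate near 9%. The stated power points to that rate only if the test is two-sided.

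The conclusion assumes one record per man, an 18 v 18 split, no dropout, and that an unqualified logistic model means maximum likelihood. The comparison is secondary: 4.6 says the sample size was set to compare standard with fusion biopsy, and neither the per-core hypothesis nor McNemar's test uses this model. It is worth correcting because correction is nearly free.

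**What to change.** In 4.6, replace the sentence on the adjusted analysis with one that states:

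- the unit is the man;
- the model is Firth penalised logistic regression, with profile-likelihood intervals and penalised likelihood-ratio tests;
- it contains PET status and one (at most two) pre-named covariates already available at entry, such as log PSA, which eligibility already requires;
- the result is exploratory.

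It would also help to state the base rates and sidedness behind the 41-point figure. Exact logistic regression would be a reasonable alternative; what matters is that the method is fixed in advance.

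The cost is a sentence or two of text and standard software, with no extra patients or procedures. The drawbacks are that fewer factors can be adjusted for and that Firth estimates shrink slightly towards no effect (for example a median of 10.0 against a true 11.2 with one covariate at 9% v 50%). The imprecision of 36 men remains: with one covariate, 17% to 22% of Firth estimates in the table were still more than twice the true value.
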